7.3.1 Sponsor-Investigator reporting: notifying the Mayo IRB

The sponsor-investigator will report to the Mayo IRB any UPIRTSOs and Non-UPIRTSOs according to the Mayo IRB Policy and Procedures.

Information collected on the adverse event worksheet and entered in the research database:

- Subject's name
- Medical record number
- Disease/histology (if applicable)
- The date the adverse event occurred
- Description of the adverse event
- Relationship of the adverse event to the research (drug, procedure, or intervention*)
- If the adverse event was expected
- The severity of the adverse event (use a table to define severity scale 1-5**)
- If any intervention was necessary
- Resolution: (was the incident resolved spontaneously, or after discontinuing treatment)
- Date of Resolution:

The sponsor-investigator will review all adverse event reports to determine if specific reports need to be made to the IRB and FDA. The sponsor-investigator will sign and date the adverse event report when it is reviewed. For this protocol, only directly related SAEs/UPIRTSOs will be reported to the IRB.

Consider the use of a table to define the Relationship of an Event to the Research and the severity of each event.

Assessment of Causality

The relationship of an AE to the Janssen Ad26.CoV2.S vaccine is a clinical decision by the sponsor-investigator (S-I) based on all available information at the time of the completion of the CRF and is graded as follows:

1. Not Related: a reaction for which sufficient information exists to indicate the etiology is unrelated to the study drug; the subject did not receive the study medication or the temporal sequence of the AE onset relative to administration of the Janssen Ad26.CoV2.S vaccine is not reasonable or the event is clearly related to other factors such as the subject's clinical state, therapeutic intervention or concomitant therapy. By definition, all solicited AEs at the injection site (local) will be considered related to the Janssen Ad26.CoV2.S vaccine administration.
2. Unlikely: a clinical event, including laboratory test abnormality, with a temporal relationship to drug administration which makes a causal relationship improbable and in which other drugs, chemicals, or underlying disease provide plausible explanations.
3. Possible: a clinical event, including laboratory test abnormality, with a reasonable time sequence to administration of the drug but which could also be explained by concurrent disease or other drugs or chemicals; information on drug withdrawals may be lacking are unclear.
4. Probable: a clinical event, including laboratory test abnormality, with a reasonable time sequence to administration of the drug, unlikely to be attributed to concurrent disease or other drugs or chemicals and which follows a clinically reasonable response on withdrawal (de-challenge): re-challenge information is not required to fulfill this definition.
5. Definite: a reaction that follows a reasonable temporal sequence from administration of the drug, or in which the drug level has been established in body fluids or tissues, that follows a known or expected response pattern to the suspected drug, and that is confirmed by improvement on stopping or reducing the dosage of the drug, and reappearance of the reaction on repeated exposure (re-challenge).

Severity Criteria

The revised NCI Common Terminology Criteria for Adverse Events (CTCAE) version 5.0 or the most current updated version will be utilized to determine the grading scales and descriptions for AE reporting. The study team and all areas where study procedures will occur will have access to a copy of the CTCAE version 5.0 or the most current updated version, and a copy can be downloaded from the CTEP website:

http://ctep.cancer.gov/protocolDevelopment/electronic_applications/ctc.htm

The severity of solicited signs and symptoms will be graded in the diary by the subjects based on the severity assessment provided in the diary as well as assessed by the investigator. (Note: severity of the measured events will be derived from the diameter [for erythema and swelling] and the temperature measurements [for fever]).

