3.6 Primary Safety Endpoints

Primary Endpoint

SAEs related to the Janssen Ad26.CoV2.S vaccine.

Secondary Endpoints

1. SAEs related to reduction in immunosuppression.
2. Any hospitalization within 2 years of randomization.
3. Microbiologically defined infectious complications.
4. Patient survival at 2 years post randomization.
5. Graft survival at 2 years post randomization.
6. Adverse events related to the Janssen Ad26.CoV2.S vaccine.
7. Adverse events related to reduction in immunosuppression (rejection, graft loss, new onset donor-specific alloantibody formation).
8. Incidence of de novo alloantibody found as SOC.
9. Occurrence and relationship of SAEs and adverse events of special interest (AESIs), medically-attended adverse events (MAAEs) (until 6 months after the last Janssen vaccination), and MAAEs leading to study discontinuation (during the entire study) for all participants.

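### Two secondary safety endpoints need events attributed to the immunosuppression reduction, but the only defined causality scale grades relation to the vaccine

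*Combined protocol and SAP*

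**What the plan says.** Section 3.1.1 randomizes 300 non-responders 1:1. All receive the vaccine, and 150 receive it after immunosuppression adjustment.

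Section 3.6 makes vaccine-related SAEs the primary safety endpoint. Two secondary items turn on the adjustment instead: item 1, "SAEs related to reduction in immunosuppression", and item 7, "Adverse events related to reduction in immunosuppression (rejection, graft loss, new onset donor-specific alloantibody formation").

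Section 7.3.1, Assessment of Causality, opens: "The relationship of an AE to the Janssen Ad26.CoV2.S vaccine is a clinical decision by the sponsor-investigator (S-I"). Five grades follow, from Not Related to Definite, all defined relative to the vaccine or study drug. Not Related includes an event clearly due to other factors, among them the subject's "clinical state, therapeutic intervention or concomitant therapy". Possible covers an event with reasonable timing "which could also be explained by concurrent disease or other drugs or chemicals".

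The same section lists a worksheet item, "Relationship of the adverse event to the research (drug, procedure, or intervention"), marked with an asterisk that no note explains. It also retains an instruction that reads like template text: "Consider the use of a table to define the Relationship of an Event to the Research and the severity of each event". No such table is given for relationship.

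**The concern.** In the randomized comparison, the vaccine is common to both arms and the immunosuppression change is the difference. The safety question specific to this trial is therefore what the change does to the graft and the patient. Items 1 and 7 pose that question in terms of relatedness, yet the scale investigators are told to use asks about the vaccine.

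Two things are at stake. Items 1 and 7 would rest on judgments made without criteria, in an open-label trial where the assessor knows the arm. The primary safety endpoint could also absorb events that belong to the adjustment. Neither is easily repaired later: causality is a clinical judgment made on the information available when the form is completed, and analysts cannot reconstruct it from the database.

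**Working it through.** The plan gives no figure to reproduce here. The check is to follow each kind of event through the 7.3.1 scale and see what reaches the 3.6 endpoints.

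| Event | Grade under 7.3.1 | Primary safety endpoint (vaccine-related SAEs) | Items 1 and 7 |
|---|---|---|---|
| Clearly due to the reduction | Not Related, through "therapeutic intervention or concomitant therapy" | Excluded, correctly | Not identified: same grade as an event unrelated to the trial |
| Reasonable timing after the vaccine, reduction also plausible | Possible | May be counted; 3.6 does not say which grades count as related | Not identified |
| Timing makes the vaccine improbable, another cause plausible | Unlikely | Probably excluded | Not identified |
| After adjustment starts, before the Segment I vaccination | Not Related, since no vaccine has been given | Excluded | Not identified |

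The last row is not a corner case. Section 5.2.1 starts the adjustment 14 days before vaccination and ends it 28 days after: 14 / (14 + 28) = 14/42, one third of the adjusted period. For Segment I patients, section 7.3 sends events between consent and first vaccination to medical history unless they are related to study procedures or to non-investigational products of the manufacturer. The schedule of events lists the adjustment, but 7.3 does not say whether it counts as a study procedure.

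Can the worksheet item supply the missing attribution? It names intervention, so it could hold the answer. But it has no grades and no criteria for the adjustment. Its single asterisk, and the double asterisk on the severity item, are most naturally resolved by the two blocks that follow, Assessment of Causality and Severity Criteria. On that reading, which is an inference, the relationship item leads back to the vaccine scale.

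The IRB rule has a related gap. Section 7.3.1 limits IRB reports to directly related events without saying related to what. The definition of unanticipated problems in 7.1 uses a possible relation to research procedures. The two differ in strength, and only the second names what the event is related to.

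Exposure to the adjustment:
- Segment I: 150 (3.1.1).
- Segment II: 0 to 250 (3.1.2), the upper limit being 150 unadjusted non-responders + 100 low responders.
- Total: 150 + 0 = 150 to 150 + 250 = 400.

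No share of events graded Not Related can be derived from the documents.

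**The case against.** The strongest reply is that the scale does its job. It asks about the vaccine, and an event caused by drug reduction is properly not related to the vaccine; the primary safety endpoint needs exactly that answer. This stands. The fault is that no second scale exists.

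It is also fair that the harms are not hidden. Section 1.5.9 has the DSMB monitor rejection and graft loss in all groups, with a pause at a 10% rejection rate. Section 7.1 names acute rejection, new donor-specific antibody and graft loss tied to the adjustment as events of significant interest. Section 3.6 includes graft survival and de novo alloantibody without attribution. Section 7.3 collects all SAEs from first vaccination whatever the cause. All of this stands, and it limits the point to attribution. The form layout is not in the documents either, so the worksheet item may offer drug, procedure and intervention as separate choices; even then, criteria would be missing.

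Three stronger readings are tempting but unsupported:
- A reader might infer that all harm from the reduction is recorded as unrelated. Only events clearly due to it are Not Related, and only with respect to the vaccine; Possible and Unlikely remain available.
- A reader might apply the rejection experience of under 10% in 1.5.9 to 150 + 100 = 250 patients and conclude that up to 25 rejections would be misgraded. That experience comes from reductions usually much longer than six weeks, the 100 in 3.1.2 is an illustration, and the product assumes every rejection is clearly due to the reduction.
- A reader might infer that these events would miss FDA reporting. Expedited reporting also turns on unexpectedness, and rejection and graft loss are described risks. Section 7.3.2 further requires notice of potential serious risks from any source.

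**Conclusion.** The point holds as a gap in attribution. Two prespecified secondary safety endpoints depend on a relationship for which the plan defines no scale or criteria, while the scale it does define concerns an exposure shared by both randomized arms. Mixed-cause events may also move adjustment harm into the primary safety endpoint if Possible counts as related.

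The size is two endpoints and 150 to 400 exposed patients; no event count is supportable. The conclusion assumes that no separate form or manual already defines relation to the adjustment, since none is included or cited for that purpose. Surveillance for the named graft events does not depend on attribution and is unaffected.

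**What to change.** 1. In 7.3.1 and on the adverse event form, record two relationships for every event: (a) to the vaccine and (b) to the immunosuppression adjustment in Segments I and II. State criteria for each, and say which grades count as related.
2. Derive the primary safety endpoint from (a) and items 1 and 7 of 3.6 from (b).
3. State what directly related refers to in the IRB rule, so that it agrees with the 7.1 definition. State whether the adjustment is a study procedure for the 7.3 reporting period.
4. Because the trial is open label, add to 6.8 a comparison of rejection, graft loss and de novo donor-specific antibody between the randomized arms regardless of attribution. Specify the period compared, since unadjusted patients who enter Segment II begin adjustment on Day 42 (5.2.2).
5. Resolve the asterisk and replace the leftover table instruction.

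The cost is one added case report form field and text edits, with no added visits or patients. It should be done before data accrue, because the judgment is made when the form is completed.

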7.3.2 Sponsor-Investigator reporting: Notifying the FDA

The sponsor-investigator will report to the FDA all unexpected, serious suspected adverse reactions according to the required IND Safety Reporting timelines, formats and requirements.

Unexpected fatal or life threatening suspected adverse reactions where there is evidence to suggest a causal relationship between the study drug and the adverse event, will be reported as a serious suspected adverse reaction. This will be reported to the FDA on FDA Form 3500A, no later than 7 calendar days after the sponsor-investigator's initial receipt of the information about the event.

Other unexpected serious suspected adverse reactions where there is evidence to suggest a causal relationship between the study drug/placebo and the adverse event, will be reported as a serious suspected adverse reaction. This will be reported to the FDA on FDA Form 3500A, no later than 15 calendar days after the sponsor-investigator's initial receipt of the information about the event.

Any clinically important increase in the rate of serious suspected adverse reactions over those listed in the protocol or product insert will be reported as a serious suspected adverse reaction. This will be reported to the FDA on FDA Form 3500A no later than 15 calendar days after the sponsor-investigator's initial receipt of the information about the event.

The sponsor-investigator must also notify the FDA (and sponsors must notify all participating investigators) in an IND safety report of potential serious risks, from clinical trials or any other source, as soon as possible, but in no case later than 15 calendar days after the sponsor determines that the information qualifies for reporting under § 312.32(c)(1)(i)-(iv).

Findings from other studies in human or animals that suggest a significant risk in humans exposed to the drug will be reported. This will be reported to the FDA on FDA Form 3500A, no later than 15 calendar days after the sponsor-investigators initial receipt of the information about the event.

7.4 Unmasking/Unblinding Procedures

Not applicable to this study as open-label, unblinded prospective design.

7.5 Stopping Rules

Discontinuation of Study Vaccination

Study vaccinations will be withheld for the reasons listed below. These participants must not receive any further doses of Janssen Ad26.CoV2.S vaccine but should remain on study for follow-up with assessments of safety and immunogenicity as indicated in the Schedules of

Activities. Additional unscheduled visits may be performed for safety/reactogenicity reasons, if needed. In case of questions, the investigator is encouraged to contact the sponsor.

- Any related AE, worsening of health status or intercurrent illnesses that, in the opinion of the sponsor-investigator, requires discontinuation from Janssen Ad26.CoV2.S vaccine
- The participant becomes pregnant
- Anaphylactic reaction following vaccination, not attributable to causes other than vaccination
- Platelet Count <75,000 prior to receiving the Janssen Ad26.COV2.s vaccine
- SAE or other potentially life-threatening (Grade 4) event that is determined to be related to Janssen Ad26.CoV2.S vaccine
- Participant received any experimental medication (including experimental vaccines other than the Janssen Ad26.CoV2.S vaccine) or received a COVID-19 vaccine or treatment
- Withdrawal of consent to receive further study vaccination
- Participant has a molecularly confirmed SARS-CoV-2 infection based on samples collected within the study (see Section 7.2.1)
- Participant previously experienced TTS, Heparin Induced Thrombocytopenia (HIT), Myocarditis or Pericarditis.

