6.1.3 Baseline Visit (-4/+1 Day)

Subjects will return to Mayo Clinic for an in-person visit. Prior to receiving the Janssen Ad26.COVID-19 vaccine, the following study procedures will be performed:

- Serum pregnancy test for females of childbearing potential.
- Platelet count

- Mechanistic Studies
- Tacrolimus, Cyclosporine and MMF serum drug levels in subjects who are receiving these drugs or who were receiving these drugs at the time of enrollment.
- Anti-SARS-CoV-2 spike protein antibody and anti-SARS-CoV-2 nucleocapsid total antibody test
- The participant will have a nephrology consult and a complete physical exam (including review of concomitant medications and immunosuppression). The nephrologist will confirm with the IS reduction group that they have complied with their new medication regimen.
- Vital Signs (heart rate, blood pressure, temperature, pulse oximetry, height and weight).
- Asked if they are experiencing any COVID-19 symptoms or have been recently tested.

Eligible subjects will be vaccinated after these procedures have been completed. The following study procedures can be completed at any time during the visit:

- Study team will record concomitant medications and therapies.
- Study team will document immunosuppression medication
- Patient Status and Graft Status
- Risk Factor Assessment (see Section 14.5)
- Safety Follow Up Questionnaires (questions related to potential GBS, TTS, myocarditis and pericarditis symptoms)
- Kidney Transplant Follow-Up Questionnaire

To differentiate symptoms potentially related to the Janssen Ad26.COV2.S vaccine, the participant will be asked about any symptoms they may currently be experiencing prior to vaccination as well as after to differentiate potential vaccine related adverse events. Then they will receive the Janssen Ad26.COV2.S vaccine during a clinical appointment. All vaccination will be monitored post vaccine for 30 minutes for potential reactions to the vaccination.

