6.2 Segment II

This segment will be evaluating the dosing of the Janssen Ad26.COv2.S vaccine with immunosuppression adjustment of patients in Segment I who were maintained on their current immunosuppression and had a lack of response at Day 28. Lack of response for this study is defined as anti-SARS-CoV-2 spike protein levels <250 U/mL.

Study procedures for Segment II will proceed in the same manner and schedule as in Segment I with the absence of screening procedures and mechanistic studies excluding the anti-SARS-CoV-2 Nucleocapsid Total Antibody test. Samples collected for the anti-SARS-CoV-2 Nucleocapsid Total Antibody test will continue to be obtained and will align with the collection and timepoints noted for the anti-SARS-CoV-2 spike protein antibody test. As all subjects will experience a reduction in IS, the Nephrologist will confirm medication compliance with the adjusted IS regimen during the Nephrology consult prior to receiving the Janssen Ad26.CoV2.S on Day 56. See Schedule of Events 3: Segment II in Section 6.6 for more details on study procedures.

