6.4 Unscheduled Visit

This visit will occur in Segments 1 and 2 if there are any medical event which would require follow up with a physician. This would be a clinical visit and contain a nephrology consult (if needed), a symptom directed physical exam, vital signs, and collection of the patient and graft status. This may include additional care if the sponsor-investigator believes it to be necessary for the health of the participant (COVID-19 surveillance, review of medications, etc.).

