6.5.1 Pre-specified Criteria for Suspected COVID-19

The criteria for suspected COVID-19 are pre-specified as follows:

- **A positive RT-PCR result for SARS-CoV-2, through a private or public laboratory independent of the study, whether symptomatic or asymptomatic**

OR

- **New onset or worsening of any 1 of the symptoms listed below, which lasts for at least 24 hours, not otherwise explained:**
 - Headache
 - Malaise (appetite loss, generally unwell, fatigue, physical weakness)
 - Myalgia (muscle pain)
 - Chest congestion
 - Cough
 - Runny nose
 - Shortness of breath or difficulty breathing (resting or on exertion)
 - Sore throat
 - Wheezing
 - Eye irritation or discharge
 - Chills
 - Fever ($\geq 38.0^{\circ}\text{C}$ or $\geq 100.4^{\circ}\text{F}$)
 - Pulse oximetry value $\leq 95\%$ which is a decrease from baseline.
 - Heart rate ≥ 90 beats/minute at rest, which is an increase from baseline
 - Gastrointestinal symptoms (diarrhea, vomiting, nausea, abdominal pain)
 - Neurologic symptoms (numbness, difficulty forming or understanding speech)
 - Red or bruised looking toes
 - Skin rash
 - Taste loss or new/changing sense of smell
 - Symptoms of blood clots: pain/cramping, swelling or redness in your legs/calves
 - Confusion
 - Bluish lips or face
 - Clinical suspicion/judgement by sponsor-investigator of symptoms suggestive for COVID-19

As several of the pre-specified criteria for suspected COVID-19 overlap with vaccine-related reactogenicity, investigators' clinical judgement is required to exclude vaccine-related events when assessing suspected COVID-19.

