6.5.2 Procedures in the Event of (Suspected) COVID-19

Procedures to be performed in the event a participant experiences signs or symptoms suggesting possible COVID-19 or a participant became aware of a positive RT-PCR test result for SARS-CoV-2 outside the study context, whether symptomatic or asymptomatic, are detailed in the Schedules of Events and captured in the eCRFs as an Unscheduled visit.

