7.2.1 COVID-19 Related Adverse Events

Identify all pertinent facts related to the COVID-19 infection including, but not limited to the following:

- Presumptive vs confirmed diagnosis. If presumptive, please update your narrative if/when diagnosis is confirmed, including timelines.
- Treatment information
- Recovery information, including timelines
- Outcome information/status

The SIC questionnaire in Section 14.3 will be utilized in situations of suspected COVID-19 infection in situations where information related to the infection is not readily available in the participant's EMR.

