8.5 Data Processing

A data coordinating group will monitor data collection and provide interim analyses to the Data Safety Monitoring Board. **We expect to complete Segment I enrollment within 6-9 months and have final data on the primary endpoint approximately 12 months from study start.** All patient outcome variables are tracked using registries set up in the “Healthy Planet” tool in the Electronic Health Record. For infection data, a registry flags patients as having an infection if a clinical diagnosis of COVID-19 was added to the problem list or a SARS-CoV-2 polymerase chain reaction test is positive. Those without laboratory confirmation are reviewed to ensure that this was appropriate (for example, an outside laboratory result not visible in our chart). External results could satisfy registry metrics if they could be identified within the interoperable framework for data sharing across the EHR, Care Everywhere (Epic Systems Corporation). A similar registry architecture captures data on vaccination data, populated from both EHR records, state health registries, and the health information exchange.

Data Security and Confidentiality

Source documents, CRFs and original consents will be stored in secured locations at Mayo Clinic. Clinical laboratory values are stored in the electronic medical record system requiring protected password access and approved use. Every individual who accesses a medical record has their activity tracked in the system. These data are monitored regularly for access and a formal policy regarding protection of personal privacy which is in place throughout Mayo Clinic.

Data Quality Assurance

Manual and computerized quality checks will occur during data collection and analyses and any discrepancies will require Case Report Form (CRF) review and validation of correct data.

Data Clarification Process

All queries will be logged and tracked electronically, as well as any corrections or justifications which are made, if applicable.

Records Retention

The sponsor-investigator will maintain records and essential documents related to the conduct of the study. These will include subject case histories and regulatory documents.

The sponsor-investigator will retain the specified records and reports for

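### The infection item in Section 7.5 has no planned trigger: it needs molecular confirmation on a study sample, and no viral molecular test is planned

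*Combined protocol and SAP*

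**What the plan says.** The list in Section 7.5 of reasons to withhold further study vaccination includes this item: "Participant has a molecularly confirmed SARS-CoV-2 infection based on samples collected within the study (see Section 7.2.1"). It sets two conditions: the confirmation must be molecular, and the sample must come from the study.

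Section 7.2.1, which the item cites, asks for the facts of a COVID-19 event (presumptive or confirmed, treatment, recovery, outcome). It adds that "The SIC questionnaire in Section 14.3 will be utilized in situations of suspected COVID-19 infection" where the medical record lacks the information. It names no specimen and no test.

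RT-PCR results appear elsewhere as follows:
- Section 6.5.1 counts as suspected COVID-19 "A positive RT-PCR result for SARS-CoV-2, through a private or public laboratory independent of the study, whether symptomatic or asymptomatic".
- Section 6.5.2 covers a participant with symptoms or one who "became aware of a positive RT-PCR test result for SARS-CoV-2 outside the study context". It sends the procedures to the Schedules of Events and an unscheduled visit.
- Section 8.5 uses a health-record registry that flags a patient when a clinical diagnosis is entered or "a SARS-CoV-2 polymerase chain reaction test is positive".

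The unscheduled visit in 6.4 consists of a nephrology consult if needed, "a symptom directed physical exam, vital signs, and collection of the patient and graft status", with further care at the sponsor-investigator's discretion.

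Before the dose, Section 6.1.3 has patients "Asked if they are experiencing any COVID-19 symptoms or have been recently tested". Section 6.2 says "Study procedures for Segment II will proceed in the same manner and schedule as in Segment I", apart from screening and mechanistic studies. Schedule 3 places COVID-19 surveillance on Day 56, before the second dose.

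**The concern.** A dosing rule should rest on evidence that the study will hold when the decision is made. Here the site will normally know before dose 2 about a positive test obtained elsewhere, because it asks. Yet such a result does not satisfy the rule as worded, and the plan includes no step that would produce a result that does. Two sites facing the same patient could decide differently and both claim to follow the protocol.

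There is a related analysis issue. Segment II has no control group, and its endpoint is a spike antibody level of at least 250 U/mL on Day 84, 28 days after the second dose. Infection or an outside COVID-19 vaccine between Day 28 and Day 84 can also raise spike antibody, so such a patient could be counted as a responder to the study dose. Section 6.8 plans logistic models of possible confounders but names neither of these.

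**Working it through.** The documents give no figure for this item, so there is none to reproduce. The check has three parts.

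**1. Is there a planned study sample that could meet both conditions?**

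| Source | Planned content | Viral molecular test? |
|---|---|---|
| 3.1.5 Study Measurements | Spike and nucleocapsid antibody | No (serology) |
| 3.1.4 Mechanistic studies | Includes one PCR assay, for T-cell receptors | No |
| 6.4 Unscheduled visit | Consult if needed, exam, vital signs, status | No |
| 7.2.1 (cited by 7.5) | Narrative and questionnaire | No |
| Schedules 1, 2A, 2B, 2C, 3 | Antibody tests, blood count, drug levels, pregnancy test, mechanistic blood | No |

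None is planned.

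**2. How many patients could fall between dose 1 and dose 2?**

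Inputs: infection rate about 10% per year (6.8, note on the incidence of COVID-19); dose 2 on Day 56 (5.2.2); Segment II size 100 as the working figure (3.1.2, 6.7) and 250 as the maximum (3.2).

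- Hazard: −ln(1 − 0.10) = 0.1054 per year.
- Probability over 56 days: 1 − exp(−0.1054 × 56/365) = 0.016, or 1.6%.
- Expected number: 100 × 0.016 = 1.6; 250 × 0.016 = 4.0.
- Reading 10% as a rate of 0.10 per year instead gives 1.5%: 1.5 of 100 or 3.8 of 250.

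The window starts at dose 1, not Day 28, because a patient infected on Days 0 to 27 whose Day 28 level is still below 250 U/mL can also go on to dose 2.

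The 10% predates vaccination programmes, and 6.8 calls the future risk unknown. Taking half and double that rate as assumptions:
- 5% per year: 1 − exp(0.1534 × ln 0.95) = 0.8%, or 0.8 of 100 and 2.0 of 250.
- 20% per year: 1 − exp(0.1534 × ln 0.80) = 3.4%, or 3.4 of 100 and 8.4 of 250.

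Here 0.1534 = 56/365.

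**3. How far could the Segment II response rate move?**

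Days 28 to 84 also span 56 days, so infection again affects about 1.6%, or roughly 2 of 100. About half of that falls after dose 2, which no rule on giving dose 2 can prevent. With the 60 responders of 100 assumed in 6.7:

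- Excluding 2 responders: 58/98 = 59.2%.
- Excluding 2 non-responders: 60/98 = 61.2%.
- Standard error: √(0.6 × 0.4/100) = 0.049, or 4.9 points.

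The shift is between −0.8 and +1.2 points. Outside vaccination cannot be sized from the documents.

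**The case against.** Several points can be made for the plan as written.

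- **Other safeguards.** Section 7.5 also bars a dose after COVID-19 treatment and allows a stop for intercurrent illness in the sponsor-investigator's opinion. Section 4.5 delays a dose for acute illness or fever, and 1.5.7 promises close monitoring and referral for treatment. This stands, and it narrows the gap to a patient who is well, untreated and known to be positive. A reader might infer that infected patients would be dosed with nothing to prevent it; the documents do not support that.
- **A study swab is possible.** Section 6.4 permits additional care, including COVID-19 surveillance, at an unscheduled visit. A swab taken there might count as a study sample. This stands too: the rule lacks a planned trigger, but it is not impossible to meet. A discretionary swab is still not a specified study test.
- **Outside laboratories are not the only source.** The registry in 8.5 also holds in-house results, and 3.7 treats laboratory results in the medical record as source data. It would be too strong to say that every RT-PCR the study receives is external. Whether an in-house clinical result counts as collected within the study is left open.
- **The narrow wording may be deliberate.** Prior infection is not an exclusion in 4.2, the parallel list in 4.4.1 has no infection item, and no purpose is stated. The documents do not show that dosing a recovered patient is harmful, and this point does not claim it. But a rule that is meant to operate needs a trigger, and one that is not should be removed.
- **Confounding is partly covered.** An outside vaccine before dose 2 already stops dosing under 7.5, so for vaccination the open period is mainly Days 56 to 84. Nucleocapsid antibody is drawn with every spike test, and 6.8 provides for confounder models. This limits the analysis issue, although neither infection nor outside vaccination is named.

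**Conclusion.** The point holds as a drafting defect with a small practical effect. The item in 7.5 depends on a test that no section or schedule plans, and its cross-reference does not supply one. As a result, a well, untreated patient with a known positive RT-PCR between the two doses is stopped only by investigator judgement.

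At the protocol's rate this concerns at most about 2 of 100 or 4 of 250 Segment II patients. It is an upper figure for that rate because it counts every infection between the doses, including those that other items would catch. It assumes a constant rate, the nominal 56-day interval, and that the pre-vaccination 10% still applies; the counts scale roughly in proportion to the rate.

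A reader might infer that the trial's main result is at risk. It is not: the randomized comparison is read on Day 28 after the first dose, before the second-dose decision. The consequence is confined to who receives dose 2 and to an uncontrolled secondary endpoint, where the expected movement is about 1 point.

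**What to change.** Reword the 7.5 item to: *documented positive SARS-CoV-2 RT-PCR from any source (study, outside laboratory or health-record registry) since the first study dose*. Cite Sections 6.5 and 8.5 in place of 7.2.1. The date limit is needed. Without it, the item would also bar patients whose only positive test predates enrolment, whom the entry criteria admit. At 10% per year and an assumed one year of prior history, that could be 0.10 × 250 = 25 patients.

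Add one sensitivity analysis: the Segment II Day 84 response rate with and without patients who, between Day 28 and Day 84, had a positive RT-PCR, new nucleocapsid antibody positivity or an outside COVID-19 vaccine.

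The cost is one wording amendment and one extra analysis, with no new tests or visits. Recent testing is already asked about, nucleocapsid antibody is drawn on Days 28, 56, 70 and 84 (Schedule 3), and outside vaccines must be recorded (5.6). The downside is that a few patients do not receive dose 2 or are flagged in the analysis.
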